2.4.5.3 Analyses of laboratory variables

The summary statistics (including number, mean, median, Q1, Q3, standard deviation, minimum and maximum) of all laboratory variables (central laboratory values and changes from baseline) will be calculated for each visit or study assessment (baseline, each postbaseline time point, last on-treatment and/or worst on-treatment value) by treatment group. For each continuous parameters listed in [Section 2.1.4.3](#), mean changes from baseline with the corresponding standard error will be plotted over time in each treatment group. This section will be organized by biological function as specified in [Section 2.1.4.3](#).

The incidence of PCSAs (list provided in Appendix A) at any time during the treatment-emergent adverse event period will be summarized by biological function and treatment group whatever the baseline level and/or according to the following baseline status categories:

- Normal/missing
- Abnormal according to PCSA criterion or criteria

For parameters for which no PCSA criteria are defined, similar table(s) using the normal range will be provided.

For PCSA analyses, the laboratory measurements obtained at either scheduled or unscheduled visits should be used; and, both the centralized and local test results should be used, as long as their available dates/time is different from each other's. Centralized data will be used preferentially to the local measures in the PCSA analyses when measurements are performed on the same date and at the same time for a given laboratory test.

Additional analyses for potential drug-induced liver injury

The following additional analyses will be performed for potential drug-induced liver injury:

- Time to onset of the initial ALT elevation ($>3 \times \text{ULN}$), AST elevation ($>3 \times \text{ULN}$) and total bilirubin elevation ($>2 \times \text{ULN}$) will be analyzed with K-M curves, presented by intervention group.
- A graph of distribution of peak values of ALT versus peak values of total bilirubin will also be presented.
- For each liver function test (eg, ALT), participants having a PCSA (eg, ALT $>5 \text{ ULN}$) will be summarized using the following categories: Returned to baseline PCSA status (or returned to value $\leq \text{ULN}$ in case of missing baseline) before last IMP dose, Returned to baseline PCSA status after last IMP dose, Never returned to baseline PCSA status, No assessment after elevation. This summary will be performed by categories of elevation (ALT $>3, >5, >10, >20 \text{ ULN}$).

2.4.5.4 Analyses of vital sign variables

The summary statistics (including number, mean, median, Q1, Q3, standard deviation, minimum and maximum) of all vital signs variables (values and changes from baseline) will be calculated

for each visit or study assessment (baseline, each postbaseline time point, last on-treatment and/or worst on-treatment value) by treatment group. For all parameters, mean changes from baseline with the corresponding standard error will be plotted over time (at same time points) in each treatment group.

The incidence of PCSAs at any time during the treatment-emergent adverse event period will be summarized by treatment group irrespective of the baseline level and/or according to the following baseline status categories:

- Normal/missing
- Abnormal according to PCSA criterion or criteria

2.4.5.5 Analyses of electrocardiogram variables

The summary statistics (including number, mean, median, Q1, Q3, standard deviation, minimum and maximum) of all ECG variables (central laboratory values and changes from baseline) will be calculated for each visit or study assessment (baseline, each postbaseline time point, last on-treatment and/or worst on-treatment value) by treatment group. For all parameters, mean changes from baseline with the corresponding standard error will be plotted over time (at the same time points) in each treatment group.

The incidence of PCSAs at any time during the treatment-emergent adverse event period will be summarized by treatment group irrespective of the baseline level and/or according to the following baseline status categories:

- Normal/missing
- Abnormal according to PCSA criterion or criteria

2.4.6 Analyses of pharmacokinetic and pharmacodynamic variables

2.4.6.1 Pharmacokinetic analyses

2.4.6.1.1 Analyses of serum concentrations of SAR231893 (REGN668)

Serum concentrations of SAR231893 (REGN668) will be summarized in the PK population using arithmetic and geometric means, SD, standard error of the mean (SEM), coefficient of variation (CV), minimum, median and maximum per sampling time. If date and/or time of the drug injection and/or sampling is missing then the concentration will not be taken into account. For drug-treated patients, where concentration values are below the lower limit of quantification (LLOQ), one-half of the LLOQ will be used. Values will be expressed in the tables with no more than three significant figures. For patients in the placebo group, concentration values are below the LLOQ will be taken into account with a plasma concentration considered equal to 0.

2.4.6.1.2 Analyses of ADA variables

The following summary will be provided based on ADA population:

- Number (%) of patients with pre-existing immunoreactivity
- Number (%) of patients with treatment-emergent ADA
- The summary statistics (including number, median, Q1, Q3, minimum and maximum) of the peak post-baseline titer for patients with treatment-emergent ADA, and patients with persistent, indeterminate and transient ADA response
- Number (%) of patient with transient treatment-emergent ADA
- Number (%) of patients with persistent treatment-emergent ADA
- Number (%) of patients with indeterminate treatment-emergent ADA
- Number (%) of patients with treatment-boosted ADA
- The summary statistics (including number, median, Q1, Q3, minimum and maximum) of the peak post-baseline titer for patients with treatment-boosted ADA
- The summary statistics (including number, mean, SD, median, Q1, Q3, minimum and maximum) of the ratio of peak post-baseline titer to baseline titer for patients with treatment-boosted ADA
- Listing of ADA peak titer levels and neutralizing antibody status
- Number (%) of patients with neutralizing antibody status

Kinetics of treatment-emergent ADA response

Number (%) of patients with treatment-emergent ADA positive response at each visit will be summarized by each treatment group.

Plot of percentage of patients with treatment-emergent ADA positive response at each visit will be provided by each treatment group.

Impact of ADA on PK

Associations between ADA variables (eg, ADA peak titers, neutralizing antibody status, treatment-emergent, persistent, indeterminate and transient response, treatment-boosted) and serum concentration of dupilumab may be explored for each dupilumab dose group. Plot of serum concentration of functional SAR231893 (REGN668) versus visit will be provided by ADA classifications for each dupilumab dose group. Individual patient plots of PK according to ADA status will be provided to determine which individuals may have had PK impacted by ADAs.

Association of ADA with clinical efficacy endpoints

Associations between the ADA variables (eg, ADA peak titers, neutralizing antibody status, treatment-emergent, persistent, indeterminate and transient response, treatment-boosted) and the primary efficacy endpoint may be explored for the dupilumab dosed group.

Association of ADA with clinical safety endpoints

Association of safety versus ADA status may be analyzed in the ADA population. The safety assessment may focus on the following events:

Severe injection site reactions last longer than 24 hours or serious injection site reactions

- Hypersensitivity reactions (SMQ (20000214) hypersensitivity narrow search confirmed by medical review)
- Anaphylactic reactions (SMQ (20000021) anaphylactic reaction narrow search)
- In response to AESI like anaphylaxis or hypersensitivity additional ADA samples closer to the event may be analyzed, based on the judgment of the medical investigator and/or medical monitor.
- Associations between ADA variables (eg, ADA peak titers, neutralizing antibody status, treatment-emergent and treatment-boosted) and safety may be explored.

2.4.6.2 *Pharmacodynamics/genomics analyses*

All biomarkers listed in [Section 2.1.6](#) will be summarized in the Safety population defined as patients who actually received at least 1 dose or part of a dose of the IMP. Baseline values will be the last value collected prior to the first IMP. Descriptive statistics (including number, mean, SD, median, Q1, Q3, min, max) of biomarkers at baseline will be summarized.

Summary plots (mean +/- standard error of the mean) on values at each visit, absolute changes from baseline and percent changes from baseline will be provided for each biomarker by treatment group and visit.

Exploratory analysis of DNA/RNA will be addressed in a separate document.

2.4.7 Analyses of health economics variables

Analyses of healthcare resource utilization will be performed outside of CSR under the responsibility of the Health Economics and Value Assessment (HEVA) department of Sanofi.

2.5 DATA HANDLING CONVENTIONS

2.5.1 General conventions

The following formulas will be used for computation of parameters.

Demographic formulas

Age is calculated as:

$$\text{Integer part of (informed consent date - birth date)/365.25}$$

Age of onset of COPD is calculated as:

$$\text{Integer part of (COPD diagnosis date - birth date)/365.25}$$

BMI is calculated as:

$$\text{Weight in kg / (height}^2 \text{ in meters)}$$

Smoking quantity (pack-year) is calculated as following:

$$\text{Number of pack-year} = (\text{packs smoked per day}) \times (\text{years as a smoker})$$

Renal function formulas

For patients ≥ 18 years old, creatinine clearance (CLcr) value will be derived using the equation of Cockcroft and Gault:

$$\text{CLcr (ml/min)} = (140 - \text{age}) \times \text{weight (kg)} \times (1 - 0.15 \times \text{sex (0-M, 1-F)}) / (0.814 \times \text{creatinine } (\mu\text{mol/L}))$$

CLcr will be calculated using the last weight measurement on or before the visit of the creatinine measurement and age at the lab sampling date. Here age is calculated as following:

$$\text{Age} = \text{integer part of (lab sampling date - birth date)/365.25}$$

2.5.2 Data handling conventions for secondary efficacy variables

Periodical average of daily efficacy endpoints at designated study days

For the daily efficacy endpoints, the time period used to calculate the periodical average at each designated study day is summarized in [Table 5](#).

Randomization day is used as the reference day (Day 1).

Table 5 - Periodical average of daily efficacy assessment

Time point	EXACT, E-RS:COPD
Day 8 (Week 1)	2-8
Day 15 (Week 2)	9-15
Day 22 (Week 3)	16-22
Day 29 (Week 4)	23-29
Day 36 (Week 5)	30-36
Day 43 (Week 6)	37-43
...	...
Day 365 (Week 52)	359-365
...	...
Day 449 (Week 64)	443-449

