- a Randomization/baseline visit is defined as Day 1. The visit schedule should be adhered to within ±1 week for the 4-week screening period, ±3 days for the randomized IMP treatment period and ±5 days for the post IMP treatment period. If more than 12 weeks since last on-site scheduled visit, then unscheduled visit is required within 3 weeks of missed scheduled visit (eg, if missed scheduled visit at Week 24, then unscheduled visit must be performed by Week 27; If missed scheduled visit at Week 36, then unscheduled must be performed by Week 39). All the assessments of the missed scheduled on-site visit will need to be carried out at the unscheduled visit.
- b All assessments at Visit 2 (Day 1) are to be conducted pre-IMP dose with the exception of the assessment of local tolerability of SC injections.
- c End-of-treatment visit: See Section 7.1.1 for patients who discontinue treatment prematurely.
- d ECG to be centrally collected & read.
- Chest X-ray to be performed unless a <6-month-old chest x-ray/chest CT/chest MR is available. In case chest-X-ray is not feasible due to local regulations, magnetic resonance imaging (MRI) will be performed.
- f IMP (Dupilumab or placebo) is to be administered every 2 weeks by patient, caregiver or healthcare professional at the patient's home or in a health care facility. Last dose will be given at Week 50. If the patient or Investigator decides not to administer IMP at home, the IMP injections can be performed at the site by way of unscheduled visits. The IMP can be administered at home after training and at least 1 IMP injection at the site and supervised by the Investigator. Patients will be monitored at the study site for a minimum of 30 minutes after injections. See Section 6.1.1 for details. If the patient is unable or unwilling to administer IMP at home, injections can be performed at the site; or arrangements can be made for qualified site personnel and/or health care professionals (eg, visiting nurse service) to administer IMP for the doses that are not scheduled to be given at the study site.

Amended Clinical Trial Protocol 03 EFC15805 - dupilumab

28-Oct-2023 Version number: 1

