- g Electronic diary is used for recording of patient's answers to the EQ-5D-5L, EXACT and SGRQ questionnaires. This handheld device is dispensed at Screening Visit 1 (including instructions for use) and recorded information is reviewed on the other indicated days. At EOT visit the electronic diary is downloaded from the device and returned to the site.
- h Complete physical examinations will include skin, nasal cavities, eyes, ears, respiratory, cardiovascular, gastrointestinal, neurological, lymphatic, and musculoskeletal systems.
- i Vital signs, including systolic and diastolic blood pressure (mmHg), pulse rate (beats per minute), body temperature (°C), and respiratory rate will be measured at screening, baseline and every subsequent on-site visit. Height (cm) will be measured at screening (Visit 1) only. Body weight (kg) will be measured at screening (Visit 1) and at EOT/EOS visits.

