2.1.3.2.2 Exploratory/Tertiary efficacy endpoints

2.1.3.2.2.1 Exacerbations of chronic pulmonary disease tool (EXACT)

The EXACT tool quantifies and measures exacerbations of COPD and assesses the symptomatic manifestations of these COPD exacerbations (see Appendix D). The instrument is a daily diary composed of a total of 14 items representing the following domains:

- Breathlessness (5 items),
- Cough and sputum (2 items),
- Chest symptoms (3 items),
- Difficulty bringing up sputum (1 item),
- Tired or weak (1 item),
- Sleep disturbance (1 item), and
- Scared or worried (1 item).

The EXACT total score assesses COPD exacerbations. The higher the score, the more severe are the symptoms.

The EXACT questionnaire is assessed daily from screening to Visit 16 (Week 52). Baseline EXACT score as well as the post-baseline weekly scores will be calculated as the mean within-patient score over the prior 7 days, with data present for a minimum of 4 of the 7 days. If fewer than 4 days of data are available in the 7-day window, the EXACT score cannot be calculated and will be considered as missing. For the exacerbation analysis, the baseline would be reset during

the study. Additional information related to computing scores and frequency, severity, and duration of events can be found in the user manual (6).

The Evaluating Respiratory Symptoms (E-RS) in COPD (E-RS: COPD) scale is a part of the EXACT tool. It is a derivative instrument used to measure the effect of treatment on the severity of respiratory symptoms in stable COPD. The E-RS utilizes the 11 respiratory symptom items contained in the 14-item EXACT.

The daily COPD RS-Total score is computed by taking the sum of the 11 items comprising the instrument. It has a range of 0 to 40, with higher values indicating more severe respiratory symptoms.

The same summation procedure is used to derive the three daily domain scores:

- COPD RS-Breathlessness (sum of items 7, 8, 9, 10, and 11; score range 0–17)
- COPD RS-Cough and Sputum (sum of items 2, 3, 4; score range 0–11)
- COPD RS-Chest Symptoms (sum of items 1, 5, 6; score range 0–12)

Like for EXACT, the baseline RS score as well as the post-baseline weekly domain and total scores are calculated as the mean within-patient score over the prior 7 days, with data present for a minimum of 4 of the 7 days. If fewer than 4 days of data are available in the 7-day window, the RS scores cannot be calculated and will be considered as missing.

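### The fixed day 359-365 window for the Week 52 E-RS score is not tied to the Week 52 visit, so a permitted early visit can leave too few diary days for a score

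*SAP*

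**What the plan says.** - **Window.** SAP 2.5.2 counts days from randomisation ("Randomization day is used as the reference day (Day 1"). Table 5 assigns days 359-365 to the row "Day 365 (Week 52".
- **Minimum data.** SAP 2.1.3.2.2.1 requires the weekly mean to be formed "with data present for a minimum of 4 of the 7 days". The consequence is explicit for E-RS: "If fewer than 4 days of data are available in the 7-day window, the RS scores cannot be calculated", and the score is then missing.
- **Visit window.** Protocol 1.3.1, footnote a, allows plus or minus "3 days for the randomized IMP treatment period".
- **End of diary.** Protocol 1.3.1, footnote g: "At EOT visit the electronic diary is downloaded from the device and returned to the site". SAP 2.1.3.2.2.1: "The EXACT questionnaire is assessed daily from screening to Visit 16 (Week 52". Protocol 8.1.2.1 adds that the diary is not completed daily after the treatment period.
- **Role of the endpoint.** Change in E-RS total score at Week 52 is eighth of the nine tests in the hierarchy of SAP 2.4.4.3. SAP Appendix L analyses it by MMRM under missing at random and labels it exploratory.

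**The concern.** The averaging window is fixed by the calendar, while data collection stops at the visit. When the visit is early but within its permitted window, the last days of the averaging window can never be filled, and the 4-of-7 rule then applies to fewer than seven obtainable days. A patient who kept the diary faithfully can lose the Week 52 score because of the appointment date.

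Other Week 52 endpoints are protected from this. SAP Table 7 accepts SGRQ on days 309-406 and pre-bronchodilator spirometry on days 337-406. E-RS has no such tolerance, and the SAP states no fallback.

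At stake is precision for a controlled endpoint. The test that follows it in the hierarchy, the exacerbation rate in the baseline FeNO subgroup, can be reached only if E-RS is significant.

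**Working it through.** **Step 1. Reproduce the plan's window.** With randomisation as day 1, Week 52 is day 52 × 7 + 1 = 365. Seven days ending there run from 365 − 6 = 359 to 365, which matches Table 5. The permitted visit is 365 ± 3, that is days 362 to 368.

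**Step 2. Count the obtainable days.** For a visit on day v, the obtainable days in the window are min(365, v − 1) − 358 if no entry is made on the visit day, and min(365, v) − 358 if one is.

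| Visit day | 362 | 363 | 364 | 365 | 366-368 |
|---|---|---|---|---|---|
| No visit-day entry | 3 | 4 | 5 | 6 | 7 |
| Visit-day entry | 4 | 5 | 6 | 7 | 7 |

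Only one cell falls below 4: a day-362 visit without an entry that day.

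**Step 3. Chance of a missing score.** Assume each obtainable day is completed independently with probability c. With k obtainable days, P(missing) = P(Binomial(k, c) < 4).

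| k | 3 | 4 | 5 | 6 | 7 |
|---|---|---|---|---|---|
| c = 0.95 | 100% | 18.5% | 2.3% | 0.2% | 0.02% |
| c = 0.90 | 100% | 34.4% | 8.1% | 1.6% | 0.3% |
| c = 0.85 | 100% | 47.8% | 16.5% | 4.7% | 1.2% |

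**Step 4. Average over visit days.** The documents give no distribution of visit days, so two are assumed: uniform over the seven days, and triangular with weights 1, 2, 3, 4, 3, 2, 1 out of 16. For example, uniform timing with c = 0.90 and no visit-day entry gives (1 + 0.344 + 0.081 + 0.016 + 3 × 0.003) / 7 = 20.7%.

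| Share missing | c = 0.95 | c = 0.90 | c = 0.85 |
|---|---|---|---|
| Uniform, no visit-day entry | 17.3% | 20.7% | 24.7% |
| Triangular, no visit-day entry | 9.1% | 12.6% | 17.0% |
| Uniform, visit-day entry | 3.0% | 6.5% | 10.6% |
| Triangular, visit-day entry | 1.5% | 3.6% | 6.7% |
| Seven days always available | 0.02% | 0.3% | 1.2% |

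If every visit falls on day 365 and no visit-day entry is made, the share at c = 0.90 is 1.6%.

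**Step 5. Information lost.** If the preceding weekly score is observed and correlates ρ with the Week 52 score, the loss for the Week 52 contrast is roughly the share missing × (1 − ρ²). The correlation is also an assumption, taken as 0.8 to 0.95.

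- Largest: 0.247 × (1 − 0.64) = 8.9%.
- Smallest: 0.015 × (1 − 0.9025) = 0.15%.

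**The case against.** **The 4-of-7 rule absorbs most of the problem.** This stands. A reader might infer that many Week 52 scores are missing by design. The documents do not support that: a score is impossible on one of the seven permitted visit days, and only if nothing is entered that day. On every other day it can be calculated, and loss depends on missed entries.

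**Evening entry is not documented for E-RS.** This also stands. SAP 2.4.2.1.1 mentions evening recording only for controller medication. Daily assessment up to Visit 16 may include the visit day, and Protocol 8.1.2.1 has questionnaires at a site visit completed before other procedures. Both cases are therefore shown.

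**Visit timing and completion are assumed.** True. The upper figures combine a uniform spread of visits with no visit-day entry.

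**The MMRM recovers the loss.** Largely, if the Week 51 score is present and the model fits. SAP 2.4.4.5.1 analyses weekly scores in the manner of Week 52 FEV₁, which implies an unstructured matrix over up to 52 visits (52 × 53 / 2 = 1,378 parameters). Whether that model can be fitted was not tested here. It is a separate question, and changing the window would not answer it.

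**Fixed, non-overlapping weeks are a coherent choice.** Agreed. That argues for keeping days 359-365 as the rule and adding only a fallback.

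**The stakes are low.** E-RS is tested only after seven earlier rejections. The primary conclusion is not affected.

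**Conclusion.** The mismatch is real and follows from the text: the window is fixed at days 359-365, the visit is permitted from day 362, and daily entry ends at the visit. Some Week 52 E-RS scores can be lost through permitted timing.

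For uniform or triangular timing and 85% to 95% daily completion, about 9% to 25% of scores are missing without a visit-day entry and 1.5% to 11% with one, against 0% to 1% with seven obtainable days. The information lost is roughly 0.1% to 9% for correlations of 0.95 to 0.8. All of it rests on assumed visit timing, independent daily completion and an assumed correlation. The loss is near zero if almost all visits fall on or after day 365.

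A reader might also infer a biased treatment comparison. Nothing in the documents suggests that visit timing differs by arm or depends on symptoms, so only a loss of precision is shown. This is a cheap improvement and not a flaw that threatens a conclusion.

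**What to change.** Keep days 359-365 as the rule and add a fallback to SAP Table 5. If the Week 52 visit falls on days 362-364 and days 359-365 hold fewer than 4 entries, the Week 52 score is the mean over the 7 calendar days ending on the visit day if an entry exists for it, and otherwise on the day before the visit. The 4-of-7 rule stays.

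The end day should be tied to the visit in this way. If it were simply the last entry found, a patient who stopped the diary long before could have an old score labelled Week 52.

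**Effect.** For visits on days 362-364, P(missing) falls to the seven-day column of Step 3. Without a visit-day entry, a day-365 visit still has six obtainable days. In the least favourable case (triangular, c = 0.85) the total becomes 0.75 × 1.2% + 0.25 × 4.7% = about 2.1%, down from 17.0%.

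**Cost.** One line in Table 5 and its derivation program, using data already collected; it should be settled before unblinding. For the affected patients the window shifts by up to 4 days (355-361 for a day-362 visit) and shares up to 4 days (355-358) with the Week 51 score, days 352-358. The SAP should state that overlap.
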